Stopping Perioperative Angiotensin II Converting Enzyme inhibitors and/or receptor blockers in major non-cardiac surgery (SPACE): a phase II, explanatory, randomised controlled trial

Statistical Analysis Plan

Version 2.0 Date: 17/03/2022

Person(s) contributing	to the analysis plan
Name(s) and	[name] (Statistician)
position(s)	[name] (Chief Investigator)
Authorisation	
Position	Chief Investigator
Name	[name]
Signature	Q
Date	17.03.2022
Position	Trial Statistician
Name	[name]
Signature	[name]
Date	17.03.2022

1. Administrative information

Trial Information

REC number:	16/LO/1495		
Trial Sponsor:	Queen Mary University of London		
Trial Sponsor reference:	011368		
	British Oxygen Company research chair award in		
Trial Funder:	Anaesthesia, administered by the National Institute		
	for Academic Anaesthesia		
ISRCTN number:	17251494		
NIHR CRN Portfolio ID number:	31645		
Protocol version (date):	Version 7.0 (14/12/2020)		

SAP revision history

Protocol version	Updated SAP version no.	Section number changed	List of changes from previous version/protocol	Author of change	Date
8.0	2.0	6	Added descriptive statistics for re-admission to hospital within 30 days of surgery and actual level of care on the first night after surgery Removed adjustment of RCRI Score in primary analysis due to not being possible to define elevatedrisk surgery using the minimisation variable planned surgical procedure which will lead to inaccuracies. We have instead included a separate descriptive table for RCRI as this will not affect the primary or secondary results.	[name]	17.03.2022

Members of the writing committee

[name] (AP) wrote the statistical analysis plan, with input from [name] (GA).

Timing of the SAP

Version 2.0 of the SAP was written after AP had access to unblinded data (i.e. trial dataset with the variables for treatment allocation included). Note that all contributors are blinded to the primary outcome as samples will be processed by an independent laboratory at the end of the trial (defined as when the last patient leaves hospital).

Remit of the SAP

The purpose of this document is to provide details of the statistical analyses and presentation of results to be reported within the principal paper(s) of the SPACE trial. It is important to set these out and to agree them in advance of inspecting the outcome data for the trial, so that data derived decisions in the analysis are avoided. Any exploratory, post hoc or unplanned analysis will be clearly identified as such in the respective study analysis report. This SAP does not include in its remit the health economic analysis which will be planned in a separate document.

2. Background and trial design

Study objectives	Primary Objective
Study objectives	To determine whether continuing perioperative Angiotensin converting enzyme inhibitor (ACE-I) and/or Angiotensin II receptor blockers (ARB) reduces the risk of myocardial injury, identified using high-sensitivity plasma troponin measurement during the first 48 hours after surgery Secondary Objectives To determine whether continuing perioperative ACE-I and/or ARB
	reduces the risk of postoperative morbidity
Study design	Phase II, multi-centre, two-arm, parallel group randomised controlled trial
Setting	Surgical services of hospitals undertaking major elective surgery
Participants	 Inclusion criteria Informed consent (no incapacitated or vulnerable adult or minors will be included) Age 60 years and over Undergoing major surgery (e.g. major joint replacement or vascular or gastrointestinal) requiring general and/or regional anaesthesia with sedation Currently taking ACE-I or combined ACE-I and ARB therapy or combination therapy where medication includes ACE-I or ARB Expected duration of surgery longer than 120 minutes American Society of Anaesthesiologists physical status grade 3 or above All female subjects must be postmenopausal, as demonstrated by clinical history, or demonstrated not to be pregnant through a preoperative pregnancy test Exclusion criteria Current participation in any other trials where care or treatment is being altered Recent myocardial infarction (within 3 months) Any condition, which in the opinion of the treating clinician, would result in the patient being harmed by the cessation
Interventions	Continue Group Patients in the continue group will continue with their ACE-I and/or ARB 72 hours prior to the day of surgery and continue for at least 48 hours after surgery. Stop Group Patients in the stop group will stop their ACE-I and/or ARB [according to half-life of each individual drug] prior to the day of surgery through to at least 48 hours after surgery.

Primary outcome measure	The primary outcome is myocardial injury, a binary variable based on plasma high sensitivity Troponin-T measured in blood samples collected immediately before the induction of anaesthesia, and then postoperative day 1± 6 hours and day 2±6 hours. The primary outcome is met under the following conditions: • Troponin-T ≥15 ng/L within 48 hours after surgery with a pre-operative value <15 ng/L OR • Troponin-T increase ≥5 ng/L within 48 hours after surgery with a pre-operative value ≥15ng/L

3. Outcome measures

Primary outcome measure

The primary outcome is myocardial injury, a binary variable based on plasma high sensitivity Troponin-T) measured in blood samples collected immediately before the induction of anaesthesia, and then postoperative day 1 ± 6 hours and day 2 ± 6 hours after surgery. The primary outcome is met under the following conditions:

- Troponin-T ≥15 ng/L within 48 hours after surgery with a pre-operative value <15 ng/L OR
- Troponin-T increase ≥5 ng/L within 48 hours after surgery with a pre-operative value ≥15ng/L

Secondary outcome measures

- Peak level of Troponin-T measured within 48 hours of surgery. Peak Troponin-T level (ng/L) will be calculated as the highest Troponin-T from the blood samples collected at 24 hours and 48 hours after surgery.
- Infection within 30 days of surgery
- Myocardial infarction within 30 days of surgery
- Acute heart failure within 30 days of surgery
- Stroke within 30 days of surgery
- Death within 30 days of surgery

Full definitions of secondary outcome measures can be found in the SPACE protocol.

4. Sample size and randomisation

Sample size calculation

Assuming incidence of postoperative myocardial injury of 50% in patients undergoing major surgery in the cessation group, a sample size of 248 patients will provide 90% power to detect as statistically significant (p<0.05) an 20% absolute risk reduction to 30% [1, 2]. Allowing for 5% withdrawal/loss to follow up, we will aim to recruit a total of 260 patients.

Randomisation procedure

Randomisation will occur after the participant has provided informed consent 72 hours before the surgical procedure is due to start. Participants are randomised to a treatment group in a 1:1 ratio using a computer-generated dynamic procedure (minimisation) with a random component. Minimisation variables are trial centre, surgical procedure category (surgery involving the gut and all other surgery) and ACE-I and/or ARB category. Each participant will be allocated with 80% probability to the treatment group that minimises between group differences in these factors among all participants recruited to the trial to date, and to the alternative group with 20% probability. To enter a patient into the SPACE trial, research staff at the site will log on to a secure web-based randomisation and data entry platform hosted by Queen Mary University of London and complete the patient's details to obtain a unique patient identification number and allocation to a treatment group. A patient's treatment group allocation will only be revealed to the person performing randomisation.

5. Analysis methods

General analysis principles

Analyses will follow the intention-to-treat principle: all randomised patients with a recorded outcome will be included in the analysis and analysed according to the treatment to which they were randomised [3, 4]. Patients will be included in the analysis, regardless of whether the treatment they received was compliant with the protocol. Definitions of what constitutes a recorded outcome for each outcome can be found in Appendix 1. Patients with missing outcome data will be excluded from the analysis. Missing data for baseline covariates to be included in the analysis model will be accounted for using mean imputation for continuous variables and the missing indicator approach will be used for missing data for categorical variables [5, 6].

For the analysis of the primary outcome, each secondary outcome, and all process measures, we will present the following information:

- The number of patients included in each analysis, by treatment group
- A summary statistic of the outcome (e.g. mean (SD), number (%)), by treatment group
- The estimated treatment effect
- A 95% confidence interval for the estimated treatment effect
- A two-sided p-value

For all analyses, a significance level of 5% will be used.

Representativeness of patients

All participating sites have been asked to keep a log of eligible patients not recruited to the trial. Reasons for non-participation will be categorised and summarised. Participation in the trial, treatment allocation and completeness of follow-up will be illustrated by a CONSORT flow diagram [7].

Baseline characteristics

Baseline characteristics will be summarised for each treatment group by the mean and standard deviation or median and interquartile range for continuous variables, and the number and percent for categorical variables. The following baseline characteristics will be summarised by treatment group:

- Demographic: age (years), gender (male/female)
- Co-morbid disease: (a) COPD; (b) asthma; (c) interstitial lung disease or pulmonary fibrosis;
 (d) ischaemic heart disease; (e) diabetes mellitus; (f) heart failure; (g) liver cirrhosis; (h) active cancer; (i) previous stoke or TIA; (j) peripheral vascular disease; (k) Hypertension; (l) any treated infections within the previous month
- Current smoker
- ASA grade (III/IV)
- Pre-operative blood test results (within 4 weeks before surgery or most recent): (a) haemoglobin (g/L); (b) creatinine (μmol/L)
- Minimisation criteria:
 - o Planned surgical procedure: (a) surgery involving the gut; (b) all other surgery
 - o Class of drug routinely taken: (a) ACE-I; (b) ARB
 - Trial centre: (a) County Durham and Darlington NHS foundation trust; (b) Plymouth hospitals NHS trust; (c) Barts Health NHS trust; (d) University college London hospitals; (e) University hospitals Bristol NHS foundation trust
- Surgical procedure performed: (a) surgery involving the gut; (b) all other surgery
- Cardiovascular medication: (a) beta-blocker; (b) calcium channel antagonist; (c) Doxazosin;
 (d) Diuretic; (e) Statin; (f) Nitrate; (g) Anti-platelet agents (h) ACE-I/ARB drugs

Analysis software

All analyses will be conducted in Stata Version 14 (StataCorp. 2015. *Stata Statistical Software: Release* 14. College Station, TX: StataCorp LP).

Analysis of primary outcome

Primary analysis

The primary outcome, myocardial injury within 48 hours after surgery, will be analysed using a mixed-effect logistic regression model, with a random intercept for the minimisation variable trial centre [8]. The model will be adjusted for minimisation variables as fixed factors which are planned surgical procedure ((a) surgery involving the gut; (b) all other surgery) and class of drug routinely taken ((a) ACE-I; (b) ARB) [9]. The model will also be adjusted for the following pre-specified baseline covariates [10-12]: age and gender (M/F). All covariates will be entered into the model as fixed factors. Age will be included as a continuous variable, assuming a linear association with the outcome [13].

When participants are randomised according to incorrect baseline information, under the ITT principle they should be analysed in their allocated treatment group, irrespective of the fact that their allocation was based on incorrect information. The incorrect baseline information should be kept in the randomisation record, as this reflects how the randomisation was performed, and the correct information documented for use in an adjusted analysis [14].

Analysis of secondary outcomes

Peak level of Troponin-T measured within 48 hours of surgery

The mean (SD) peak level of Troponin-T measured within 48 hours of surgery will be reported within each treatment group. Differences between the groups in the mean peak level troponin-t will be analysed using multilevel linear regression – adjusted for the same baseline variables as the adjusted analysis of the primary outcome. We will also adjust for baseline pre-operative Troponin-T as a continuous variable.

Infection within 30 days of surgery

Infection within 30 days of surgery will be analysed using a mixed-effect logistic regression model with a random intercept for the minimisation variable trial centre. The model will be adjusted for minimisation variables planned surgical procedure ((a) surgery involving the gut; (b) all other surgery) and class of drug routinely taken ((a) ACE-I; (b) ARB).

The expected event rate for this outcome is low, and as such we have reduced the number of covariates included in the model to avoid over-stratification.

Myocardial infarction within 30 days of surgery

The number (%) will be presented in each treatment group. An exact unadjusted logistic regression will be performed if 10 or more events are reported. No statistical analysis will be performed if there are fewer than 10 events.

Acute heart failure within 30 days of surgery

The number (%) will be presented in each treatment group. An exact unadjusted logistic regression will be performed if 10 or more events are reported. No statistical analysis will be performed if there are fewer than 10 events.

Stroke within 30 days of surgery

The number (%) will be presented in each treatment group. An exact unadjusted logistic regression will be performed if 10 or more events are reported. No statistical analysis will be performed if there are fewer than 10 events.

Death within 30 days of surgery

The number (%) will be presented in each treatment group. An exact unadjusted logistic regression will be performed if 10 or more events are reported. No statistical analysis will be performed if there are fewer than 10 events.

Strategy for analysis of primary and secondary outcomes if model fails to converge

If the statistical models for any of the primary or secondary outcomes do not converge, then the following steps will be taken:

- 1. The model will be fitted without a random intercept for trial centre
- 2. As above, but excluding any additional covariates apart from minimisation variables
- 3. As above, but also excluding minimisation variables.

Plan in case of over-stratification

When adjusting for covariates in the primary analysis or secondary analysis models where the outcome is binary, if there is a category within that covariate where no events have occurred in either of the treatment groups, the statistical model will exclude all patients within this category. To overcome this, this category will be merged with another category; this will be decided by the chief investigator who will be blinded to results. This will apply to covariates with three or more categories. However, if all but one category within that covariate have no events recorded in one of the treatment groups then we will exclude this covariate from the model.

Sensitivity analysis

The amount of missing primary outcome data is anticipated to be minimal but will be accounted for in a sensitivity analysis if missing data is greater than 5%. The primary analysis will be repeated once assuming that all patients in the continue group with missing outcomes did not experience myocardial injury, and all patients in the stop group with missing outcomes experienced myocardial injury. The analysis will then be repeated again with the opposite assumptions. This will then give the absolute range of how much the results could change if the data were complete. This will also assess the robustness of our analysis of the primary outcome under the assumption that data is missing-not-at-random (MNAR).

6. Other analyses, data summaries and graphs

Clinical management

Clinical management for the continue group and stop group will be summarised but not subjected to statistical testing. Numbers (%) and means (SD) or medians (IQR) will be provided separately for each group. The continue and stop groups will be compared for the following clinical management characteristics:

- Surgical technique
- Anaesthetic technique
- Planned and actual level of care on the first night after surgery
- Blood pressure during surgery
- Intravenous fluids during surgery

Process measures

Summary measures will be presented separately for each treatment group. All patients with recorded data will be included in the summary. Formal statistical analysis will not be performed. Duration of hospital stay after surgery (days) and total duration of critical care stay within 30 days of surgery (days) will be summarised using mean (SD) and median (IQR). Re-admission to hospital within 30 days of surgery will be presented as number (%).

Safety analyses

Adverse events and serious adverse events will be presented as a number (%) by treatment group. All patients with a recorded outcome will be included in the summary. In addition to this, 'other' adverse events will be reported separately if prevalence is more than 5% across all participants in the trial.

Protocol deviations

Numbers and percentages of protocol deviations will be reported. The following protocol deviations will be reported: (a) Patient in the stop group did receive ACE-I and/or ARB; (b) Patient in the continue group did not receive ACE-I and/or ARB; (c) other deviation. We will report the number of patients in each treatment group with at least one of the above protocol deviations. In addition to this, 'other' protocol deviations will be reported separately of prevalence is more than 5% in the trial.

Complications within 30 days after surgery

The number and percentage of patients experiencing each of the following complications will be presented by treatment allocation. These summaries will not be subjected to any statistical testing. These complications are as follows:

- Cardiac complications
- Respiratory complications
- Infective complications
- Other complications
- Acute kidney injury

Revised Cardiac Risk Index for Pre-Operative Risk (RCRI)

The Revised Cardiac Risk Index for Pre-Operative Risk [15] evaluates the risk of cardiac complications after noncardiac surgery. The six factors used to calculate this score are: elevated-risk surgery, history of ischemic heart disease, history of congestive heart failure, history of cerebrovascular disease, preoperative treatment with insulin and pre-operative creatinine >2mg/dL / 176.8 mcmol/L. The RCRI score (0-6) will be calculated for both groups. The component variables will be tabulated separately for reference. The RCRI Score and its individual components will only be summarised for patients who have all components of the score complete.

References

- 1. Ackland, G.L., et al., *Early elevation in plasma high-sensitivity troponin T and morbidity after elective noncardiac surgery: prospective multicentre observational cohort study.* British Journal of Anaesthesia, 2020. **124**(5): p. 535-543.
- 2. Gillies, M.A., et al., *Perioperative myocardial injury in patients receiving cardiac output-guided haemodynamic therapy: a substudy of the OPTIMISE Trial*. British Journal of Anaesthesia, 2015. **115**(2): p. 227-233.
- 3. White, I.R., et al., *Strategy for intention to treat analysis in randomised trials with missing outcome data.* BMJ, 2011. **342**: p. d40.
- 4. Montori, V.M. and G.H. Guyatt, *Intention-to-treat principle*. CMAJ: Canadian Medical Association journal = journal de l'Association medicale canadienne, 2001. **165**(10): p. 1339-1341.

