Anastomotic leak					
Perforation of viscus					
Gastro-intestinal bleed					
Other postoperative haemorrhage					
Any other complication					
Acute kidney Injury - no. (%)					

Table 6: Process measures

Process measures		Number of patients with available data - no. (%)		Summary measure	
	Stop (n=XXX)	Continue (n=XXX)	Stop	Continue	
Re-admission to hospital within 30 days of surgery – no. (%)					
Duration of hospital stay after surgery (days)					
Mean (SD)					
Median (IQR)					
Number of patients admitted to a critical care unit - no. (%)					
Total duration of critical care stay within 30 days of surgery (days)					
Mean (SD)					
Median (IQR)					

Table 7:Adverse events

Adverse Events - no. (%)	Stop (n=XXX)	Continue (n=XXX)
Patients with ≥ 1 adverse event		
Total number of adverse events		
Number of adverse events per patient		
0		
1		
2		
3		
Type of adverse event		
Hypertension ^a		
Hypotension ^b		
Acute kidney injury ^c		
Other		

^a Defined as Systolic BP>180mmHg from randomisation until 48 hours after surgery, Diastolic BP> 100mmHg from randomisation until 48 hours after surgery

Table 8: Serious Adverse Events

Serious Adverse Events	Stop (n=XXX)	Continue (n=XXX)
Patients with ≥1 SAE		
Total number of SAEs		
Type of SAE		
Death		
Life-threatening complication		
Prolonged existing hospital stay or required re-		
admission		
Significant disability or incapacity		
Other important medical event		

^b Defined as requiring pressor via central venous access from randomisation until 48 hours after surgery

^c Defined as in the absence of haemorrhage/sepsis (KIDIGO grades 1-4) within 30 days after surgery

Table 9: Revised Cardiac Risk Index for Pre-Operative Risk

Revised Cardiac Risk Index for Pre-Operative	Number of patients with available data - no. (%)		Summary measure	
Risk	Stop (n=XXX)	Continue (n=XXX)	Stop	Continue
Score - no. (%)				
0 - 2				
3 - 6				
Components - no. (%)				
Elevated-risk surgery				
History of ischemic heart disease				
History of congestive heart failure				
History cerebrovascular disease				
Pre-operative treatment with insulin				
Pre-operative creatinine > 2 mg/dL / 176.8 mcmol/L

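### The pre-operative troponin used as a 'baseline' covariate in the peak Troponin-T model is measured after randomisation, so the planned estimate is not the total effect of allocation

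*SAP*

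**What the plan says.** - **Covariate.** SAP section 5, under the peak Troponin-T outcome, takes the covariates of the primary analysis and adds one: "We will also adjust for baseline pre-operative Troponin-T as a continuous variable".
- **Time of the sample.** Section 3 defines the primary outcome from troponin "measured in blood samples collected immediately before the induction of anaesthesia", with further samples on postoperative days 1 and 2. The SAP describes no earlier troponin.
- **Time of randomisation.** Section 4: "Randomisation will occur after the participant has provided informed consent 72 hours before the surgical procedure is due to start".
- **Start of the strategies.** Section 2: "Patients in the stop group will stop their ACE-I and/or ARB [according to half-life of each individual drug] prior to the day of surgery". For the other arm: "Patients in the continue group will continue with their ACE-I and/or ARB 72 hours prior to the day of surgery".
- **Outcome.** Section 3: "Peak Troponin-T level (ng/L) will be calculated as the highest Troponin-T from the blood samples collected at 24 hours and 48 hours after surgery".
- **Missing covariates.** Section 5, General analysis principles: "Missing data for baseline covariates to be included in the analysis model will be accounted for using mean imputation for continuous variables".
- **Reporting.** The mean (SD) peak is given by arm. Pre-operative troponin is not in the section 5 list of baseline characteristics or in Tables 1 and 4 of Appendix 3.

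**The concern.** Adjusting for a covariate measured before randomisation sharpens the estimate without changing what is estimated, because allocation cannot have affected it. That protection is lost when the covariate is measured after the arms have diverged. The induction sample falls in that position, so the word 'baseline' is a mislabel.

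The consequence is a change of target. Section 5 promises an intention-to-treat analysis, which compares the two strategies from the point of allocation. A model that holds induction troponin fixed compares the arms only on what happens beyond that level. It is the only effect estimate planned for peak troponin, unless the model fails to converge and the fallback steps drop covariates. Because the induction value is not tabulated by arm, a reader could not tell whether the two targets differ.

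The imputation rule adds a smaller problem. Filling gaps with the overall mean relies on the covariate being independent of allocation, which randomisation guarantees only for variables fixed beforehand.

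**Working it through.** **1. Order of events, from the SAP alone.** Consent and randomisation (72 hours before surgery) → stop group stops (before the day of surgery) → first troponin (just before induction) → surgery → troponin on days 1 and 2. The covariate comes third, after allocation and after the exposures separate. The SAP ties the stopping time to each drug's half-life and gives no hours, so the length of the interval is not known beyond the 72-hour limit.

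**2. What the adjustment removes.** Let T = 1 for stop, P the induction value and Y the peak. For least squares,

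adjusted effect = unadjusted effect − fitted slope of Y on P × difference in P between arms.

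The other covariates and the random centre intercept do not alter the principle. If P = m + d·T + error and Y = a + b·P + c·T + error, the total effect is c + b·d and the adjusted effect is c.

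**3. Illustration.** The SAP gives no troponin levels, so there is no figure of its own to reproduce on this point; its sample size of 248 concerns the primary outcome and does not enter. Every input here is an assumption: pre-randomisation level mean 14 and SD 8 ng/L, measurement SD 2, intercept 5, residual SD 8, later effect c = 3 ng/L, and 400,000 simulated patients per row. Effects are stop minus continue, in ng/L.

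| b | d | c + b·d | Total | Adjusted for induction value | Adjusted for pre-randomisation value |
|---|---|---|---|---|---|
| 0.5 | 0 | 3.0 | 2.98 | 2.98 | 2.98 |
| 0.8 | 0 | 3.0 | 3.01 | 3.03 | 3.03 |
| 0.5 | 2 | 4.0 | 3.95 | 2.95 | 3.95 |
| 0.8 | 2 | 4.6 | 4.60 | 3.00 | 4.60 |
| 1.0 | 2 | 5.0 | 5.04 | 3.01 | 5.02 |

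With d = 0 all the estimates agree. With d = 2 the induction-adjusted fit omits b × 2, and adjustment for a true baseline does not.

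**4. If the early shift carries into the peak in full, whatever the slope.** The fitted slope is then b × 64/(64 + 4) = 0.94b, that is 0.47, 0.75 and 0.94 for b = 0.5, 0.8 and 1.0. The simulated share of the shift removed was 45–48%, 75–77% and 91–96%. For b = 0.8 and d = 2 the total was 5.03 and the adjusted estimate 3.51.

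**5. Direction.** Keep c = 3 and b = 0.8 but let d = −2. The total is 3 − 1.6 = 1.4 and the adjusted effect is 3. Here adjustment moves the estimate away from no difference.

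**6. Missing induction values.** Appendix 1 sets the peak to missing only if both postoperative values are absent. A patient with no induction sample therefore stays in the peak model with an imputed covariate, although the same patient, with both postoperative values present, is set to missing for the primary outcome. The SAP does not say how many such patients to expect.

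**7. Primary outcome.** Its model has no troponin covariate, but the same induction value is the reference in the definition. The postoperative threshold is 15 ng/L if P < 15, and P + 5 if P ≥ 15. A rise before induction leaves the threshold unchanged for a patient still below 15 ng/L, and raises it only for one at or above 15 ng/L at induction.

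**The case against.** The best defence is that the reference is intended. The stated aim is injury in the 48 hours after surgery, and a value taken just before induction separates new injury from chronic elevation. Adjusting the peak for that value fits this aim and gains precision, and the crude means by arm will be visible. This stands as a reason to keep the adjusted fit. It does not make the covariate a baseline variable, and crude means without a confidence interval do not replace an effect estimate.

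It is also fair that the size is hypothetical and that the sentence at issue governs one secondary outcome. Both points stand.

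Four stronger readings are tempting, and the documents do not support them:

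- **That the adjustment removes any effect before surgery.** It removes the fitted slope times the shift, which can be less than the whole (step 4).
- **That the bias must be towards no difference.** This needs the effects before and after induction to share a sign (step 5), and the SAP does not establish that.
- **That the plan itself expects troponin to change before surgery, because Table 7 counts hypertension as** "Systolic BP>180mmHg from randomisation until 48 hours after surgery". That is a window for safety events and says nothing about troponin.
- **That the primary result is compromised.** The threshold moves only for patients at or above 15 ng/L at induction. A patient who stays below 15 ng/L, and whose rise carries forward, becomes more likely to count as an event. Counting any postoperative value of 15 ng/L or more would be no remedy, since it would class chronic elevation as injury.

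**Conclusion.** The point holds as one of labelling and estimand for peak Troponin-T. The covariate is measured after randomisation and after the stop group has stopped, so the planned estimate is the effect beyond the pre-induction level. It differs from the total effect of allocation by the fitted slope times any difference between arms at induction.

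That gap is zero if stopping leaves induction troponin unchanged. Otherwise its size and sign cannot be derived from the SAP; the ng/L figures above show the mechanism and do not predict this trial's result. The conclusion rests on the SAP's stated timing and on there being no pre-randomisation troponin, since none is described. For the primary outcome the only remark warranted is that it shares the same reference value. This is a cheap, worthwhile improvement to one secondary analysis, and it leaves the primary analysis as planned.

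**What to change.** - Rename the covariate 'pre-induction Troponin-T'.
- Report the peak comparison without it, with a 95% CI, as the intention-to-treat (total-effect) estimate. Keep the other covariates as planned.
- Report the adjusted fit alongside, labelled as the effect beyond the pre-induction level.
- Tabulate pre-induction troponin by arm, with the difference and 95% CI. This also lets readers judge whether the primary outcome's reference differed between arms.
- Exempt this variable from the mean-imputation rule and fit the adjusted model in patients with an observed value.

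The cost is a few lines of SAP text, one extra model and one table entry, with no new data. The fit without the covariate will have a wider interval, which is why the adjusted fit stays. Section 1 says that contributors remain blinded to the primary outcome because samples are processed after the trial ends, so the change can be fixed before any troponin result is seen.
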